5.1.2.2 ARIA-H

Dose reduction: Patients who develop >10 ARIA-H cumulatively will receive a lower dose of the study drug. Of note, patients who received a reduced dose of blinded study drug can start the OLE phase with the full dose of 60 mg/kg crenezumab.

Study drug discontinuation: Patients who develop > 15 ARIA-H cumulatively will be permanently discontinued from the study drug.

Cumulative ARIA-H is the sum of ARIA-H at baseline (of Study BN29552 or BN29553) and newly detected ARIA-H during the studies.

The rules in Sections 4.1.2 and 5.1, coupled with frequent MRI monitoring and collection of CNS symptoms, are put in place by the Sponsor to ensure safety while maximizing benefit for patients.

5.1.3 Management of Patients Who Experience Specific Adverse Events

5.1.3.1 Hypersensitivity and Infusion Reactions

Crenezumab will be administered to patients under close medical supervision in a setting with access to appropriate emergency equipment and staff who are trained to monitor and respond to medical emergencies. In the event that a patient experiences a mild infusion-related reaction, the infusion will be halted. Once the reaction has resolved, the infusion rate will be resumed at half of the most recently used rate (██████████). Patients who experience a moderate infusion-related reaction (e.g., fever or chills) should have the infusion stopped immediately and should receive aggressive symptomatic treatment. The infusion should not be restarted before all symptoms have disappeared, and then it should be restarted at half the initial rate. Patients who experience serious or severe hypersensitivity reactions (e.g., hypotension, mucosal involvement) should not receive additional study drug.

5.1.3.2 Amyloid-Related Imaging Abnormalities

To date, there has been limited clinical experience ARIAs with crenezumab; however, data from studies on other MAb treatments reveal that ARIA events tend to occur early after treatment initiation, are dose dependent and APOE4 dependent, are manageable with MRI monitoring, and do not lead to significant adverse outcomes.

All clinical trials with crenezumab include APOE4 genotyping, MRI safety monitoring, and an ARIA-based dose-intervention algorithm.

5.1.4 Additional Safety Monitoring

Laboratory tests, including hematology and chemistry, will be performed throughout the OLE study. ECGs will be recorded regularly (see Section 4.5.8). *Complete* examinations will be performed as required *per the schedule of activities* to assess physical and neurologic events that are not consistent with normal disease progression.

Symptom-directed physical and neurologic examinations may be done at any other visit as needed to assess the safety of the participant. The C-SSRS will be used for prospective suicidality assessment. Pregnancy testing will be performed at each visit in women of childbearing potential. Samples to assess immunogenicity will be collected throughout the OLE study.

5.2 SAFETY PARAMETERS AND DEFINITIONS

Safety assessments will consist of monitoring and recording adverse events, including serious adverse events and adverse events of special interest, performing protocol-specified safety laboratory assessments, measuring protocol-specified vital signs, and conducting other protocol-specified tests that are deemed critical to the safety evaluation of the study.

Certain types of events require immediate reporting to the Sponsor, as outlined in Sections [5.2.2](#) and [5.2.3](#).

5.2.1 Adverse Events

According to the ICH guideline for Good Clinical Practice, an adverse event is any untoward medical occurrence in a clinical investigation subject administered a pharmaceutical product, regardless of causal attribution. An adverse event can therefore be any of the following:

- Any unfavorable and unintended sign (including an abnormal laboratory finding), symptom, or disease temporally associated with the use of a medicinal product, whether or not considered related to the medicinal product
- Any new disease or exacerbation of an existing disease (a worsening in the character, frequency, or severity of a known condition; see Sections [5.3.5.9](#) and [5.3.5.10](#))
- Recurrence of an intermittent medical condition (e.g., headache) not present at baseline
- Any deterioration in a laboratory value or other clinical test (e.g., ECG, X-ray) that is associated with symptoms or leads to a change in study treatment or concomitant treatment or discontinuation from study drug
- Adverse events that are related to a protocol-mandated intervention, including those that occur prior to assignment of study treatment (e.g., screening invasive procedures such as biopsies)

5.2.2 Serious Adverse Events (Immediately Reportable to the Sponsor)

A serious adverse event is any adverse event that meets any of the following criteria:

- Is fatal (i.e., the adverse event actually causes or leads to death)
- Is life threatening (i.e., the adverse event, in the view of the investigator, places the patient at immediate risk of death)

This does not include any adverse event that had it occurred in a more severe form or was allowed to continue might have caused death.

- Requires or prolongs inpatient hospitalization (see Section [5.3.5.11](#))

- Results in persistent or significant disability/incapacity (i.e., the adverse event results in substantial disruption of the patient's ability to conduct normal life functions)
- Is a congenital anomaly/birth defect in a neonate/infant born to a mother exposed to study drug
- Is a significant medical event in the investigator's judgment (e.g., may jeopardize the patient or may require medical/surgical intervention to prevent one of the outcomes listed above)

The terms "severe" and "serious" are not synonymous. Severity refers to the intensity of an adverse event (e.g., rated as mild, moderate, or severe, or according to National Cancer Institute Common Terminology Criteria for Adverse Events; see [Table 3](#)); the event itself may be of relatively minor medical significance (such as severe headache without any further findings).

Severity and seriousness need to be independently assessed for each adverse event recorded on the eCRF.

Serious adverse events are required to be reported by the investigator to the Sponsor immediately (i.e., no more than 24 hours after learning of the event; see Section [5.4.2](#) for reporting instructions).

5.2.3 Adverse Events of Special Interest (Immediately Reportable to the Sponsor)

Adverse events of special interest are required to be reported by the investigator to the Sponsor immediately (i.e., no more than 24 hours after learning of the event; see Section [5.4.2](#) for reporting instructions). Adverse events of special interest for this study include the following:

- Cases of potential drug-induced liver injury that include an elevated ALT or AST in combination with either an elevated bilirubin or clinical jaundice, as defined by Hy's Law (see Section [5.3.5.7](#))
- Suspected transmission of an infectious agent by the study drug, as defined below:

Any organism, virus, or infectious particle (e.g., prion protein transmitting transmissible spongiform encephalopathy), pathogenic or non-pathogenic, is considered an infectious agent. A transmission of an infectious agent may be suspected from clinical symptoms or laboratory findings that indicate an infection in a patient exposed to a medicinal product. This term applies only when a contamination of the study drug is suspected.

- Pneumonia: In the Phase II program, a numerical imbalance in pneumonia cases was observed, with more events reported in crenezumab-treated patients versus placebo-treated patients. It is of paramount importance to carefully document any pneumonia cases and other serious respiratory infections that occur in this study, by means of providing all relevant information required by the eCRF. A chest X-ray is required under the following circumstances:

Serious and non-serious pneumonia

Serious and non-serious lower respiratory tract infections

Serious upper respiratory infections

In addition, whenever possible, additional relevant investigations should be conducted (e.g., WBC counts, pathogen identification by means of hemocultures, bronchoalveolar lavage).

When a pneumonia case is diagnosed, a blood sample for fluorescence-activated cell-sorting analysis must be collected as soon as feasible for the site and the patient.

5.2.4 Selected Adverse Events

To further elucidate potential clinical implications of ARIA findings, patients will be asked if they experience CNS adverse events up to 1 week before each MRI assessment is performed. The eliciting of these adverse events should be according to Section 5.3.2. The adverse events collected in this prospective fashion will be distinct from other adverse events and summarized separately in the Clinical Study Report. Additional data on associated symptoms (as defined on the eCRF) and safety MRI scans will be collected for the following selected adverse events:

- ARIA-E: ARIAs suggestive of vasogenic edema and sulcal effusions
- ARIA-H deposition: ARIAs suggestive of mH and hemosiderin deposits

5.3 METHODS AND TIMING FOR CAPTURING AND ASSESSING SAFETY PARAMETERS

The investigator is responsible for ensuring that all adverse events (see Section 5.2.1 for definition) are recorded on the Adverse Event eCRF and reported to the Sponsor in accordance with instructions provided in this section and in Sections 5.4–5.6.

For each adverse event recorded on the Adverse Event eCRF, the investigator will make an assessment of seriousness (see Section 5.2.2 for seriousness criteria), severity (see Section 5.3.3), and causality (see Section 5.3.4).

5.3.1 Adverse Event Reporting Period

Investigators will seek information on adverse events at each patient contact. All adverse events, whether reported by the patient or noted by study personnel, will be recorded in the patient's medical record and on the Adverse Event eCRF.

After informed consent has been obtained but prior to initiation of study drug, only serious adverse events caused by a protocol-mandated intervention (e.g., invasive procedures such as biopsies, discontinuation of medications) should be reported (see Section 5.4.2 for instructions for reporting serious adverse events).

After initiation of study drug, all adverse events will be reported until 4 elimination half-lives after the last dose of study drug and collected on the occasion of the safety follow-up visit (16 weeks after the last dose of study drug).

Instructions for reporting adverse events that occur after the adverse event reporting period are provided in Section 5.6.

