Study BN40031 is an open-label extension (OLE) study (dosing crenezumab at 60 mg/kg IV every 4 weeks [Q4W] for all participants) to the two randomized, double-blind, multinational, *parent* Phase III efficacy studies BN29552 (CREAD) and BN29553 (CREAD2) that investigate crenezumab at a dose of 60 mg/kg IV Q4W compared with placebo over a 2-year treatment period in patients with pAD or mild AD (mAD) dementia.

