1.3.3 Efficacy

An exploratory objective of this OLE study is to investigate the effect of crenezumab on the underlying disease process and course.

The purpose of Studies BN29552 and BN29553 is to establish the efficacy and safety of crenezumab in patients with pAD to mAD who may or may not be treated concurrently with approved symptomatic treatments for AD, over a treatment period of 104 weeks (26 doses). This DBTP was selected to demonstrate an enduring clinical benefit of crenezumab treatment on the basis of the mechanism of action and available data to date. Crenezumab may slow clinical decline rather than provide improvement over baseline.

There is considerable scientific and clinical interest in understanding the impact of the intervention under study on the underlying disease process. It has been proposed that demonstration of a disease-modifying effect (rather than a reversible "symptomatic" effect) may be achieved in studies using a two-period design (Leber 1997; see [Figure 1](#)).

Figure 1 Randomized Start Design

Therefore, an exploratory randomized start analysis is proposed, using the 2-year DBTP in Studies BN29552 and BN29553 as Period 1 (i.e., Treatment Initiation Group 1 in the

[figure not shown]
above diagram), and 1 or 2 year(s) of treatment in Study BN40031 as Period 2 (i.e., Treatment Initiation Group 2 in the above diagram). The intent is to demonstrate that patients who received placebo treatment in Period 1 will not achieve in the medium term the same clinical benefit as those patients who received active drug treatment in Period 1. Period 2 has to provide sufficient time for crenezumab to exert its effect on the patient group who previously received placebo. At the same time, it is important to keep the amount of missing data low to enable a robust analysis. The duration of Period 2 (1 or 2 years) is to be confirmed in the Statistical Analysis Plan (SAP).

The efficacy assessments in Study BN40031 will use the same scales as in the prior Phase III studies with the CDR-SB being the primary efficacy endpoint for this exploratory two-period design.

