3.2 STUDY DESIGN

All patients who are enrolled in the OLE study will receive crenezumab 60 mg/kg administered by IV infusion Q4W.

Data collected at Week 105 of the DBTP of Studies BN29552 and BN29553 and results from a coagulation blood test taken before the first OLE infusion will be used to assess patient eligibility for the OLE study. This Week 105 data will also be used as OLE baseline data.

Prior to administering the first infusion in the OLE, eligibility will be ensured by reviewing Week 105 assessment results (*including MRI results*), *OLE screening* coagulation blood test results, and any other significant patient changes.

Once a patient is identified as eligible for the OLE study, the following will occur:

- Patients can receive the first infusion of crenezumab at any time on or up to 8 weeks after the Week 105 visit of the double-blind studies. Any extensions to this period must be approved by the Sponsor. Sites can arrange an infusion visit as soon as *eligibility assessment results* are available (including MRI results and results from the coagulation test) to assess OLE eligibility. Details of the visit schedule and associated assessments are given in [Appendix 1](#).
- The day that the first dose of crenezumab is administered will be Visit 1, Week 1 of the OLE.
- On Visit 1, Week 1 of OLE (i.e., the first open-label infusion of crenezumab), safety assessments must be done as indicated in the schedule of activities (see [Appendix 1](#)).

For details on the schedule of activities, see [Appendix 1](#). For details on the length of the study, see Section [3.3](#).

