5.4.2 Reporting Requirements for Serious Adverse Events and Adverse Events of Special Interest

5.4.2.1 Events That Occur prior to Study Drug Initiation

After informed consent has been obtained but prior to initiation of study drug, only serious adverse events caused by a protocol-mandated intervention should be reported. Investigators should *report* to the Sponsor or its designee immediately (i.e., no more than 24 hours after learning of the event).

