5.6 ADVERSE EVENTS THAT OCCUR AFTER THE ADVERSE EVENT REPORTING PERIOD

The Sponsor should be notified if the investigator becomes aware of any **serious** adverse event that occurs after the end of the adverse event reporting period (defined as 16 weeks after the last dose of study drug), if the event is believed to be **related** to prior study drug treatment. These events should be reported through use of the Adverse Event eCRF. However, if the EDC system is not available, the investigator should report these events directly to the Sponsor or its designee, either by faxing or by scanning and emailing the paper Clinical Trial Serious Adverse Event/Adverse Event of Special Interest Reporting Form using the fax number or email address provided to investigators.

5.7 EXPEDITED REPORTING TO HEALTH AUTHORITIES, INVESTIGATORS, INSTITUTIONAL REVIEW BOARDS, AND ETHICS COMMITTEES

The Sponsor will promptly evaluate all serious adverse events and adverse events of special interest against cumulative product experience to identify and expeditiously

communicate possible new safety findings to investigators, IRBs, ECs, and applicable health authorities based on applicable legislation.

To determine reporting requirements for single adverse event cases, the Sponsor will assess the expectedness of these events using the following reference document:

- Crenezumab Investigator's Brochure
- *PET Ligand Investigator's Brochures*

The Sponsor will compare the severity of each event and the cumulative event frequency reported for the study with the severity and frequency reported in the applicable reference document.

Reporting requirements will also be based on the investigator's assessment of causality and seriousness, with allowance for upgrading by the Sponsor as needed.

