6. STATISTICAL CONSIDERATIONS AND ANALYSIS PLAN

The safety analysis population will include all patients who consented to the OLE study, including those who enrolled in the OLE but did not receive open-label treatment. The intent-to-treat (ITT) population includes all patients who consented to the OLE study and received at least one dose of open-label treatment.

Safety will be assessed by monitoring adverse events, clinical laboratory evaluations, clinical assessments such as ECG and vital signs measurements, MRI evaluations and immunogenicity as measured by ADAs. Patients will be analyzed according to actual treatment received. All safety data will be summarized using descriptive statistics.

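### Between OLE consent and the first OLE dose, the protocol reports only procedure-caused SAEs, although former-crenezumab patients dosed on schedule are still within its own post-dose reporting periods and no study is named as responsible

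*Combined protocol and SAP*

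**What the plan says.** Section 5.3.1 restricts reporting after OLE consent: "prior to initiation of study drug, only serious adverse events caused by a protocol-mandated intervention" are to be reported. Section 5.4.2.1 repeats that "only serious adverse events caused by a protocol-mandated intervention should be reported". In Appendix 1 the adverse event row is blank in the OLE screening column and starts at Visit 1.

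Section 3.2 sets the length of the window: "Patients can receive the first infusion of crenezumab at any time on or up to 8 weeks after the Week 105 visit". It adds: "Any extensions to this period must be approved by the Sponsor". No upper limit on extensions is given.

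For time after a dose of study drug, the plan gives three reporting periods:

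- Section 5.6: an adverse event reporting period "defined as 16 weeks after the last dose of study drug".
- Section 5.3.1: four elimination half-lives, with collection at the 16-week visit.
- Section 5.4.2.2: 8 weeks for SAEs and AESIs.

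Section 6 puts every consenting patient in the safety population, "including those who enrolled in the OLE but did not receive open-label treatment". Section 6.4 defines that population differently: patients who completed the double-blind period, had at least one dose of parent study drug, and entered the OLE.

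**The concern.** The pre-dose rule is the usual one for screening patients who have never had the drug. Here about half of those screened come from the crenezumab arm of a parent study. The protocol requires reporting for weeks after an OLE dose, but its own text does not require it for the same interval after the same drug and dose given in the parent study.

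The events affected are ones the protocol singles out. Pneumonia is an AESI (Section 5.2.3), and Section 1.3.7 promises close monitoring of pneumonia and deaths. Death reporting is tied to the adverse event reporting period (Section 5.3.5.8). Before the first OLE dose, a death or pneumonia not caused by a study procedure has no OLE reporting rule.

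There is also a counting problem. Under the Section 6 population, a patient who consents and is never dosed because of an intervening event is in the denominator, while that event is not reportable in the OLE.

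**Working it through.** **Number of patients.** Section 6.1 estimates about 925 OLE patients. 1500 × (1 − 0.35) × (1 − 0.05) = 926.25, which reproduces it. Assuming equal retention by arm, 926.25 / 2 = about 463 former-crenezumab patients.

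**Last parent dose.** Section 1.3.3 describes parent treatment "over a treatment period of 104 weeks (26 doses"), and Section 1.1 gives the interval as every 4 weeks. Doses at Weeks 1, 5, … make the 26th dose fall at Week 1 + 25 × 4 = Week 101.

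**Time since last dose in the unextended window (Week 105 to 113).** 105 − 101 = 4 weeks at the start and 113 − 101 = 12 weeks at the end.

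**Against the plan's three periods:**

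| Period after last dose | Ends at parent week | Part of the 8-week window inside |
|---|---|---|
| 16 weeks (5.6) | 101 + 16 = 117 | all, with 4 weeks to spare |
| 4 half-lives (5.3.1); half-life 17–26 days (1.2.5), so 68–104 days or 9.7–14.9 weeks | about 110.7 to 115.9 | all at 26 days; at 17 days the last 12 − 9.7 = 2.3 weeks fall outside |
| 8 weeks, SAEs and AESIs (5.4.2.2) | 101 + 8 = 109 | the first 4 weeks |

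A first OLE dose more than 12 weeks after Week 105, which is an extension of more than 4 weeks, lies beyond 16 weeks. Patients who stopped parent treatment early but completed Week 105 may enter (Section 3.1) and may already be beyond 16 weeks.

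**Illustrative size if the parent studies captured nothing.** The rates are the Phase II crenezumab figures: 16.3% with an SAE (Section 1.2.3.1) and 1.7% with serious pneumonia (Section 1.2.3.3). Observation was 68 weeks of treatment plus 4 or 16 weeks of follow-up, so 72 to 84 weeks. With a constant hazard h = −ln(1 − p)/T, the expected number of patients is 463 × (1 − exp(−h × gap)).

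| Mean gap | Person-years | Patients with an SAE (T = 84 to 72) | Serious pneumonias (T = 84 to 72) |
|---|---|---|---|
| 4 weeks | 463 × 4/52 = 36 | 3.9 to 4.6 | 0.38 to 0.44 |
| 8 weeks | 463 × 8/52 = 71 | 7.8 to 9.1 | 0.76 to 0.88 |

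The 8-week row requires every patient to use the unextended maximum. Counting only time inside the 8-week SAE/AESI period limits exposure to the 4-week row.

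**The case against.** The strongest reply is that the parent studies collect these events. Section 1.3.2 says that OLE safety assessments, adverse event reporting included, match those of the parents. If the parents also follow patients for 16 weeks, a Week 101 dose is covered to Week 117, past the end of the unextended window. This stands as a reason not to claim loss. It does not close the point. The parent protocols are not among the documents and may treat roll-over patients differently. In the Phase II programme, patients who rolled over had only 4 more weeks of safety monitoring, against 16 for the others (Section 1.2.3.1). Those are other studies, but a similar rule here would end at about Week 105, where this window opens.

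Three further replies have weight:

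- **The 16-week period is not the only yardstick.** For SAEs and AESIs, Section 5.4.2.2 sets 8 weeks, which covers only half the window.
- **Most gaps may be short.** Section 3.2 lets sites dose once eligibility results are in, and the restriction runs from OLE consent, not from Week 105.
- **Persisting events are separable.** A reader might infer that an event starting in the window would be counted as new on open-label drug. Section 5.1 requires start and end dates for each recorded event, so an event that is recorded can be separated. That remedy does not reach events that are never recorded, or patients who are never dosed.

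Section 5.3.1 also opens by saying that all adverse events go on the eCRF, and Section 4.5.1 keeps a screening log with reasons for failure. The first is narrowed by the pre-dose sentence that follows it. The second is not an adverse event record with seriousness and causality.

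**Conclusion.** The point holds as a gap in the OLE protocol's own rules, and it is worth correcting. The pre-dose restriction is stated twice, the schedule has no adverse event mark at OLE screening, and no OLE text says which study is responsible for the window or how its events enter the OLE safety analysis. For a former-crenezumab patient dosed on schedule, the whole unextended window is inside 16 weeks and its first half is inside 8 weeks.

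Two stronger readings are not supported. One is that safety events are actually lost. That depends on parent protocols that cannot be seen. The other is that every former-crenezumab patient is still within 16 weeks of a dose. Early stoppers, and patients whose window is extended by more than 4 weeks, may not be.

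The size is modest and conditional: about 4 to 5 patients with an SAE and 0.4 serious pneumonias at a 4-week mean gap, and about 8 to 9 and up to 0.9 at the unextended maximum. This assumes no parent capture, equal retention by arm, dosing on schedule, a constant hazard, and Phase II rates from lower doses in mild to moderate disease. The denominator problem arises under the Section 6 population. Whether it arises under Section 6.4 depends on what entering the OLE means, so the two definitions must be reconciled.

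**What to change.** - **Reporting rule.** In Sections 5.3.1 and 5.4.2.1, require all SAEs and AESIs from OLE consent to the first OLE dose to be recorded regardless of cause, including for patients never dosed. Require other adverse events as well where the parent reporting period has ended. State which study covers any days between Week 105 and a later OLE consent.
- **Schedule.** Add an adverse event mark to the OLE screening column of Appendix 1.
- **No duplicates.** Where the parent study is still collecting, report the event once there and link it to the OLE record.
- **Analysis.** Tabulate these events as post-parent, pre-OLE by parent treatment received, apart from OLE treatment-emergent events.
- **Reconcile.** Align the 16-week, 4-half-life and 8-week reporting periods, and the safety populations of Sections 6 and 6.4.

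The cost is protocol wording, one schedule mark, one derivation rule, modest extra data entry and some cross-study reconciliation. Before the first infusion, sites already review Week 105 results and any significant change in the patient (Section 3.2).
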